#### 9.2.3 Subject Eligibility

#### 9.2.3.1 Inclusion Criteria

- Females diagnosed with FH
- Confirmed pregnancy during the study observation period
  - Pregnancies identified retrospectively but within the study period will be included
  - Multiple pregnancies, occurring in the same woman within the study period, will all be included (as separate pregnancies)
- Provided informed consent to follow-up in this study, for subject and their infant(s) born during the study observation period

#### 9.2.3.2 Exclusion Criteria

There are no exclusion criteria

#### 9.2.4 Matching

Not applicable

#### 9.2.5 Baseline Period

The index date is the date of diagnosis of pregnancy. The baseline period covers subject history prior to the index date. Demographic factors and all relevant medical and clinical history at diagnosis of pregnancy will be reported as baseline subject status.

#### 9.2.6 Study Follow-up

Follow-up duration may differ for each individual subject, depending on the outcome of pregnancy: Initial baseline information will be recorded at confirmation of pregnancy and the subject will be followed for outcome of pregnancy **and**, **if breastfeeding following a live birth, until termination of breastfeeding**. Information on pregnancy outcome, and on infant health **and development up to** 12 months after delivery, will be captured.

#### 9.3 Outcomes - Variables

Information available for each subject on all variables will be reported by study site staff in the study-specific database held by the sponsor. The original data source will be patient (maternal – infant) records, from routine follow-up of subjects:

- Maternal Data:
  - Demographics:
    - Country of residence
    - Age (at start of pregnancy, categorized into  $\leq$  19, 20-24, 25-29, 30-34, 35-39, 40-44,  $\geq$  45 year age categories)
    - Education (highest level)
    - Occupation
    - Height and weight (to calculate body mass index, categorised into < 20, 20-24, 25-29, ≥ 30 kg/m^2 body mass index categories)
  - Current pregnancy history:
    - Date of last menstrual period
    - Estimated date of delivery
    - Number of fetuses
    - Treatment for infertility

CONFIDENTIAL

- Medical history:
  - FH diagnosis status and method of diagnosis
  - Presence of significant comorbid conditions (hypertension, diabetes mellitus, epilepsy, other)
  - o Family history of congenital disorders
- Obstetric history:
  - Number of previous pregnancies and outcome
  - Previous maternal pregnancy complications
  - Previous fetal/neonatal abnormalities
  - History of subfertility
- Medications (product, dose, dose dates) taken within 3 months prior to or during pregnancy (excluding medication routinely administered during labour/delivery) and/or breast-feeding
- Lipid levels (triglycerides, total cholesterol, LDL-C, HDL-C)
- Congenital anomaly including congenital abnormality or malformation as defined by European Surveillance of Congenital Anomalies (EUROCAT) (See Appendix E for full list)
- Complications of pregnancy:
  - Pre-eclampsia
  - Gestational diabetes
- Outcomes of pregnancy: (See Appendix F for further definition):
  - Live birth (with / without congenital anomaly)
  - Neonatal death (with / without congenital anomaly)
  - Stillbirth (with / without congenital anomaly)
  - Elective termination (with / without congenital anomaly)
  - Miscarriage (with / without congenital anomaly)
  - Spontaneous abortion
  - Ectopic pregnancy
  - Molar pregnancy
- Mode of delivery:
  - Normal vaginal delivery
  - Operative vaginal delivery
  - Vaginal breech delivery
  - Caesarean section
- Complications of delivery:
  - Abnormal Cord gas
  - Fetal heart rate abnormalities
  - Abnormal amniotic fluid

- Blood transfusion resulting from post-partum haemorrhage;
- Thromboembolism
- Infant Data:
  - Infant status at delivery:
    - Infant(s) sex
    - Gestational age
    - Birth weight
    - Apgar score
  - Infant outcomes until 12 months of age:
    - Weight growth
    - Developmental delay (not meeting the usual developmental milestones during the first 12 months of age)
    - Hospitalisations (total number of days hospitalised; number of hospitalisation episodes during the first 12 months)
    - Chronic medication (defined as medication prescribed for a period of 4 weeks or more)
    - Breastfeeding (date of start/stop, exclusive breastfeeding [Yes/No])
- Exposure Variables:
  - Exposure to Repatha® (duration of exposure, doses, dose dates) within 15 weeks prior to conception and/or during pregnancy and/or whilst breast-feeding. In adult subjects a single dose of Repatha® constitutes exposure. In infants, exposure may occur in utero and/or via breast milk, within 15 weeks following the date of Repatha® dosing in the mother.

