#### 9.5 Study Size

The study will collect data on all pregnancies and births in females diagnosed with FH and identified via the specialist centres/networks, where the patient consents to participate. Based on a conservative estimated FH prevalence of 1 in 500, and a national diagnosis rate varying between 70% and 1% (Nordestgaard 2013), the number of subjects identified for inclusion in this study is not expected to be large. The EMA guideline EMEA/CHMP/203927/2005 "GUIDELINE ON RISK ASSESSMENT OF MEDICINAL PRODUCTS ON HUMAN REPRODUCTION AND LACTATION: FROM DATA TO LABELLING" assumes an overall incidence of birth defects of 3% in order to derive the number of first trimester pregnancies exposed to a medicinal product that is needed to exclude a certain level of risk. The Guideline further states that if no increased incidence of malformations is observed within at least 300 first trimester-exposed, prospectively collected pregnancies with known pregnancy outcomes (births or fetopathological examinations) then the conclusion might be reached that the medicinal product is not responsible for a 10-fold or more increase of the overall incidence of malformations. In accordance with the Guideline, this study will endeavour to enrol 300 pregnancies exposed to Repatha in the first trimester in order to meet the primary objective of this study. The maximum number of unexposed pregnancies will be limited to a ratio of 2 unexposed to 1 exposed; ie, the maximum will be 600 unexposed pregnancies. In addition, the maximum of unexposed pregnancies originating from a single country will be limited to the minimum of N = 150 or tenfold the expected proportion of births out of the combined total of live births as reported by the relevant Bureaus of Statistics in the participating countries (Appendix H). For example, the observed number of live births in Norway in 2017

represented 1.5% of the births across all participating countries. Therefore, no more than N = 88 (10 x 1.5% = 15% of 600) unexposed pregnancies will originate from Norway. The observed number of United Kingdom births represents 19.6% of all 2017 live births across all countries; tenfold 19.6% of 600 would exceed the target of 600, therefore the number of unexposed pregnancies from the United Kingdom will be capped at N=150. This will ensure we enrol as many unexposed pregnancies as possible whilst avoiding that unexposed pregnancies will originate from a single country only.

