## Appendix F. Pregnancy Outcome Definitions\*

Pregnancy outcome: the end products of pregnancy which include three main categories:

- Fetal death, termination of pregnancy and live birth.
- Fetal death (intrauterine death, in utero death): death prior to complete expulsion or extraction from its mother of a product of conception, irrespective of the duration of pregnancy; the death is indicated by the fact that after such separation the fetus does not show any evidence of life (WHO ICD 10).

Early fetal death (before 22 completed weeks of gestation) comprises ectopic pregnancy and miscarriage and late fetal death (after 22 completed weeks of gestation) is known as stillbirth.

- Ectopic pregnancy: extrauterine pregnancy, early fetal death most often in the Fallopian tube.
- Miscarriage: spontaneous abortion, molar pregnancy.
- Termination of pregnancy (induced abortion, elective abortion): artificial interruption of pregnancy.
- Live birth: the complete expulsion or extraction from its mother of a product of conception, irrespective of the duration of the pregnancy which, after such separation, breathes or shows any evidence of life. (WHO ICD 10).
- Gestational age or length: the duration of gestation is measured from the first day of the last normal menstrual period. Gestational age is expressed in completed days or completed weeks (eg, events occurring 280 to 286 days after the onset of the last menstrual period are considered to have occurred at 40 weeks of gestation).
- Last menstrual period (abbreviation LMP): according to international consensus, the gestational age is measured from the first day of the LMP.
- Birth weight: the initial weight of the infant at birth.
- Pre-term birth (previous term: premature birth): less than 37 completed weeks (less than 259 days) of gestation.

Term birth: from 37 to less than 42 completed weeks (259 to 293 days).

- Post-term birth: 42 completed weeks or more (294 days or more).
- Low birth weight: less than 2,500 gram (up to and including 2,499 g) of body weight of the newborn at birth.
- Intrauterine growth retardation (small for gestational age): the observed weight of a live born infant or size of a fetus is lower than expected on the basis of gestational age.

\*EMEA/CHMP Guideline on Exposure to Medicinal Products During Pregnancy

			1	Fiming of Rep	oatha ® expos	ure		

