		Exposed but stopped prior			Exposed at conception and during 1 st trimester	Exposed	Exposure during breastfeeding	
	Unexposed (N = x)	to conception (N = x)	trimester (N = x)	trimesters (N = x)	trimesters (N = x)	pregnancy (N = x)	only (N = x)	breastfeeding (N = x)
	(N – X) n (%)	(N – X) n (%)	(N – X) n (%)	(N – X) n (%)	(N – X) n (%)	(N – X) n (%)	(N – X) n (%)	(N – X) n (%)
Pregnancies enrolled pre-partum								
All outcomes	x (x.x)	x (x.x)	x (x.x)	x (x.x)	x (x.x)	x (x.x)	x (x.x)	x (x.x)
Live birth without congenital anomaly	x (x.x)	x (x.x)	x (x.x)	x (x.x)	x (x.x)	x (x.x)	x (x.x)	x (x.x)
Live birth with congenital anomaly	x (x.x)	x (x.x)	x (x.x)	x (x.x)	x (x.x)	x (x.x)	x (x.x)	x (x.x)
Neonatal death without congenital anomaly	x (x.x)	x (x.x)	x (x.x)	x (x.x)	x (x.x)	x (x.x)	x (x.x)	x (x.x)
Neonatal death with congenital anomaly	x (x.x)	x (x.x)	x (x.x)	x (x.x)	x (x.x)	x (x.x)	x (x.x)	x (x.x)
Stillbirth without congenital anomaly	x (x.x)	x (x.x)	x (x.x)	x (x.x)	x (x.x)	x (x.x)	x (x.x)	x (x.x)
Stillbirth with congenital anomaly	x (x.x)	x (x.x)	x (x.x)	x (x.x)	x (x.x)	x (x.x)	x (x.x)	x (x.x)
Miscarriage without congenital anomaly	x (x.x)	x (x.x)	x (x.x)	x (x.x)	x (x.x)	x (x.x)	x (x.x)	x (x.x)
Miscarriage with congenital anomaly	x (x.x)	x (x.x)	x (x.x)	x (x.x)	x (x.x)	x (x.x)	x (x.x)	x (x.x)
Termination of pregnancy without congenital anomaly	x (x.x)	x (x.x)	x (x.x)	x (x.x)	x (x.x)	x (x.x)	x (x.x)	x (x.x)
Termination of pregnancy with congenital anomaly	x (x.x)	x (x.x)	x (x.x)	x (x.x)	x (x.x)	x (x.x)	x (x.x)	x (x.x)
Ectopic pregnancy	x (x.x)	x (x.x)	x (x.x)	x (x.x)	x (x.x)	x (x.x)	x (x.x)	x (x.x)
Molar pregnancy	x (x.x)	x (x.x)	x (x.x)	x (x.x)	x (x.x)	x (x.x)	x (x.x)	x (x.x)
Pregnancy continuing at time of data cut-off	x (x.x)	x (x.x)	x (x.x)	x (x.x)	x (x.x)	x (x.x)	x (x.x)	x (x.x)
Pregnancies enrolled post-partum	x (x.x)	x (x.x)	x (x.x)	x (x.x)	x (x.x)	x (x.x)	x (x.x)	x (x.x)
All outcomes	x (x.x)	x (x.x)	x (x.x)	x (x.x)	x (x.x)	x (x.x)	x (x.x)	x (x.x)
Live birth without congenital anomaly	x (x.x)	x (x.x)	x (x.x)	x (x.x)	x (x.x)	x (x.x)	x (x.x)	x (x.x)
Live birth with congenital anomaly	x (x.x)	x (x.x)	x (x.x)	x (x.x)	x (x.x)	x (x.x)	x (x.x)	x (x.x)
Neonatal death without congenital anomaly	x (x.x)	x (x.x)	x (x.x)	x (x.x)	x (x.x)	x (x.x)	x (x.x)	x (x.x)
Neonatal death with congenital anomaly	x (x.x)	x (x.x)	x (x.x)	x (x.x)	x (x.x)	x (x.x)	x (x.x)	x (x.x)

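### Miscarriages, terminations and stillbirths are classed only as with or without congenital anomaly, with no state for unknown or unexamined

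*Supplement*

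**What the plan says.** Among the outcomes of pregnancy, Section 9.3 lists "Miscarriage (with / without congenital anomaly"), "Elective termination (with / without congenital anomaly") and "Stillbirth (with / without congenital anomaly"). It also lists "Spontaneous abortion" on its own line, without an anomaly split. The definitions in Appendix F fold that category into miscarriage: "Miscarriage: spontaneous abortion, molar pregnancy".

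The Appendix G template carries the same pairs, with rows such as "Miscarriage without congenital anomaly" and "Termination of pregnancy without congenital anomaly" beside their with-anomaly counterparts. Its only row for an unresolved pregnancy is for one still continuing at data cut-off. Section 9.7.1.1 calls the template an example.

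Section 9.5 adopts the target of 300 from an EMA guideline. It reports that the guideline's conclusion rests on "prospectively collected pregnancies with known pregnancy outcomes (births or fetopathological examinations").

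Four other statements bear on the point:
- The Abstract (Variables) restricts data collection to routine visits.
- Sections 9.3.2 and 9.3.4 apply independent adjudication to reported anomalies.
- Sections 9.7.2.1 and 9.7.2.2 rule out imputation.
- Section 9.9.3 does not expect outcome information to be missing.

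**The concern.** For a live birth followed to 12 months, saying that no anomaly was found normally reflects an observation. For a pregnancy loss it does so only if someone looked, by pathology, fetal examination or an informative prenatal scan. The variable list and the template do not separate a loss that was examined and found normal from one that was never examined. Adjudication cannot recover the difference, because it tests reported anomalies and never a reported absence.

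Two things are at stake. First, the without-anomaly loss rows could mix observed negatives with unknowns, and any anomaly proportion taken over all pregnancies would be diluted. The study is descriptive and plans no sensitivity analysis (Section 9.7.2.5), so the tabulated proportion is the result. Second, Section 9.5 rests the sample size on pregnancies whose outcome is known through birth or fetopathological examination. Without a record of examination, the final report cannot say how many of the exposed pregnancies qualify.

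**Working it through.** **Where could an unexamined loss go?**
- Section 9.3, miscarriage, termination, stillbirth: with or without anomaly only.
- Section 9.3, spontaneous abortion: no split. Appendix F makes it part of miscarriage and Appendix G has no row for it, so it does not serve as an unknown category.
- Appendix G, continuing pregnancies: cannot hold a completed loss.
- Sections 9.7.2.1 and 9.7.2.2: no imputation, but no rule for a blank status and no stated denominator once some are blank.

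If the table is filled as drawn, an unexamined loss is either entered as without anomaly or left out of the split rows uncounted.

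**The plan's own figures.** Section 9.5 takes 300 from the guideline without alpha, power or formula, so there is no derivation to reproduce, and the number is not disputed here. At the 3% background incidence quoted there, 300 × 0.03 = 9 expected cases (exact 95% interval for 9/300: 1.4% to 5.6%). The standard error is √(0.03 × 0.97 / 300) = 0.98 percentage points.

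**Illustration.** The documents give neither the share of pregnancies lost (L) nor the share of losses unexamined (u). Assume L = 10-30% and u = 50-100%, with a true anomaly proportion of 3.0% in losses and births alike.
- Unknown status = 300 × L × u
- Known status = 300 − unknown
- Proportion shown if unknowns count as anomaly-free = 3.0% × known / 300
- Enrolment needed for 300 of known status = 300 / (1 − L × u), rounded up

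| L | u | Unknown | Known | Shown | Enrolment for 300 known |
|---|---|---|---|---|---|
| 10% | 50% | 15 | 285 | 2.85% | 316 |
| 20% | 80% | 48 | 252 | 2.52% | 358 |
| 30% | 100% | 90 | 210 | 2.10% | 429 |

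The understatement runs from 0.15 to 0.90 points, or 5% to 30% in relative terms.

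**If anomalies are commoner in losses.** This is a further assumption. Take L = 20%, u = 80%, 10% anomalies in losses and 3% otherwise. The true figure is 0.8 × 3% + 0.2 × 10% = 4.4%. The figure shown is 0.8 × 3% + 0.2 × 0.2 × 10% = 2.8%.

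**If unknowns are left out instead.** With equal 3% risk the proportion is unbiased (for example 0.03 × 252 / 252 = 3.0%), but the base falls to between 285 and 210, and nothing in the template would show it.

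**The case against.** The strongest reply is that the plan never says unknown status is scored as negative. Section 9.3 promises to report the information available, missing data are not imputed, and Sections 9.6 and 9.9.3 provide for queries on omissions. A site could leave the field blank. Appendix G is only an example. The eCRF and its completion guideline are not shown and may offer an unknown option; the worksheets in Appendix I do so for other items.

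Much of this stands. A reader might infer that every loss must be scored one way or the other, and that unknowns will be reported as anomaly-free. The documents do not support that: it is one possible result of filling the tables as drawn, not a stated rule. A reader might also assume that most early losses go unexamined. No figure in the documents says so. But the reply does not remove the gap. The two-state split is in the Section 9.3 variable list as well as the example table. A blank would still need a row, a count and a denominator rule.

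The scope is also narrower than it may look. Section 8.1 words the primary objective around infants, although the outcome measure in Section 9.3.2 is broader. Appendix G shows live births in their own rows, so those counts are unaffected, and no pooled anomaly rate is specified. The concern bears on the loss rows and on any figure taken over all pregnancies. It is weaker for stillbirth, which Appendix F places after 22 completed weeks, than for early loss.

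Finally, the guideline text in Section 9.5 is a condition for drawing a conclusion from 300 pregnancies, not a scoring rule. The two-state split does not contradict it. It leaves the study unable to show that the condition is met.

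**Conclusion.** The point holds as a gap in classification and reporting. Section 9.3 and the Appendix G example have no state for unknown or unexamined anomaly status, and nothing records whether a loss was examined. Unexamined losses may therefore be counted as anomaly-free or disappear uncounted, and compliance with the standard cited in Section 9.5 cannot be shown.

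No stated figure is wrong, and the size is not known from the documents. The illustrative shortfalls at a uniform 3.0% risk all lie below one standard error of 0.98 points. They are nevertheless systematic: more enrolment at the same loss and examination rates would not shrink them. They depend wholly on the assumed rates, on uniform risk, and on unknowns being counted as negative. This is worth mending because it touches how the main outcome is read and costs little, but it does not invalidate the study.

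**What to change.** 1. In Section 9.3 and Appendix G, give miscarriage, termination and stillbirth three states: with anomaly; examined, without anomaly; anomaly status unknown or not examined.
2. Add one eCRF item, read from existing notes, on whether a pathology or fetal examination or an informative prenatal scan exists.
3. Show the number unknown in each exposure column.
4. Report the anomaly proportion among pregnancies of known status beside the all-pregnancy figure, with both denominators stated. State how many of the first-trimester-exposed pregnancies meet the Section 9.5 standard.

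The cost is one more eCRF item and a few more table rows. No new procedure is needed. The drawback is that fewer pregnancies will count as having known anomaly status, so the distance to 300 may look larger than an enrolment count suggests.

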#### 9.3.1 Exposure Assessment

Exposure to Repatha® in the 15 weeks (ie, 5 half-lives of Repatha®) prior to or during pregnancy or breast-feeding will be entered by site staff into study-specific electronic case report forms and will be reported descriptively by dose and dates of administration. Exposure will be counted in doses of Repatha®.

The study population comprises females in Europe, South Africa and Australia diagnosed with FH and who are either pregnant or breast-feeding during the study period, and who provide informed consent to participate in the study, if applicable according to local requirements. Their infants will also be followed to the age of 12 months, following consent by the mother (if applicable per local regulations).

(Note: The therapeutic strategy assigned to each patient enrolled in the study will not be specified within this study protocol. Instead, it will be decided according to

routine clinical practice, hence the decision for medicinal prescription will be clearly dissociated from the decision to include the patient in the study).

#### 9.3.2 Outcome Assessment

Outcome Measures:

- The primary outcome measure is congenital anomaly. Any incidence of congenital anomaly will be diagnosed and classified by the study site Investigator, or by the subject's treating physician (eg, an obstetrician, paediatrician, neonatologist) if this is not the Investigator, and reported on the study-specific eCRF. Supporting documentation will be requested to enable independent adjudication of the diagnosis, by an external expert not participating as a study investigator. Where supporting documentation is not held at the same clinic/hospital/institution as the study site, contracts will be executed to allow sharing of medical records, as necessary.
- Secondary outcome measures include:
  - Pregnancy outcomes (live birth(s), stillbirth, spontaneous loss, elective termination, ectopic pregnancy, complications of pregnancy (eg, pre-eclampsia, gestational diabetes)
  - Delivery outcomes (mode of delivery; complications including requirement for blood transfusion, thromboembolism, fetal distress, amniotic fluid abnormality)
  - Infant status at delivery: gender; gestational age; Apgar score; birth weight
  - Infant outcomes at 6 and 12 months post-delivery (including growth, hospitalisation, chronic medication)

The secondary outcome measures will be reported on the study-specific eCRF, from information entered into the subject's notes as part of routine follow-up. Where supporting documentation is not held at the same clinic/hospital/institution as the study site, contracts will be executed to allow sharing of medical records, as necessary.

Adverse outcomes requiring a clinical diagnosis of congenital anomaly will be subject to the same independent adjudication as the primary outcome.

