#### 9.7.2.7 Stratified Analysis

For the secondary objective of describing health and developmental outcomes in infants up to 12 months of age, analyses will be stratified according to whether the infant was exposed to Repatha® (in the 15 weeks prior to conception or in the first trimester of pregnancy, in the second or third trimester of pregnancy, and/or whilst breast-feeding). In addition, a stratified analysis will be conducted by exposure to other lipid modifying therapies (including statins, PCSK9 inhibitors, CETP inhibitors, and others).

In addition, data obtained from retrospective and prospective subject identification will be reported separately (to account for the possibility that subjects enrolled retrospectively may differ from those enrolled prospectively).

Results from mothers are to be presented using the following columns: (i) 'unexposed', (ii) 'exposed but stopped prior to conception', (iii) 'exposure in 1st trimester (up to 15 weeks)', (iv) 'exposure in 2nd/3rd trimesters', (v) 'exposed at conception and during 1st trimester but stopped during 2nd/3rd trimesters, (vi) 'exposed throughout pregnancy', (vii) 'exposure during breastfeeding only', and (viii) 'exposure anytime during pregnancy and up to 15 weeks, and breastfeeding'. Columns will not be mutually exclusive.

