Exposure is classified as beginning at 15 weeks prior to conception (5 halflives of Repatha), and a single dose of Repatha at any time during pregnancy or breastfeeding is classified as exposure

Section 6: Endpoint definition and measurement	Yes	No	N/A	Page Number(s)
6.1 Does the protocol describe how the endpoints are defined and measured?	$\boxtimes$			Sctn 9.2.2
6.2 Does the protocol discuss the validity of endpoint measurement? (e.g. precision, accuracy, sensitivity, specificity, positive predictive value, prospective or retrospective ascertainment, use of validation sub-study)	$\boxtimes$			Sctn 9.2.2

Comments:

Endpoints will be reported verbatim, coded in ICD10-BPA according to Eurocat classification and independently adjudicated where congenital anomaly is the outcome

Section 7: Confounders and effect modifiers	Yes	No	N/A	Page Number(s)
7.1 Does the protocol address known confounders? (e.g. collection of data on known confounders, methods of controlling for known confounders)				
7.2 Does the protocol address known effect modifiers? (e.g. collection of data on known effect modifiers, anticipated direction of effect)				

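### Pre-eclampsia and gestational diabetes have no specified onset date and are tabulated by dosing over the whole pregnancy, so the event can help decide the exposure column

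*Supplement*

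**What the plan says.** Section 9.3 has the heading "Complications of pregnancy" with pre-eclampsia and gestational diabetes beneath it as bare items. Section 9.3.2 repeats them as a secondary outcome: "complications of pregnancy (eg, pre-eclampsia, gestational diabetes". Neither section asks for a date or week of diagnosis. The same variable list does ask for dates elsewhere, including last menstrual period, start and stop of breastfeeding, and Repatha dosing: "duration of exposure, doses, dose dates) within 15 weeks prior to conception".

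Exposure is broad. The window is "within 15 weeks prior to conception and/or during pregnancy and/or whilst breast-feeding", and the ENCePP checklist (Appendix B) adds that "a single dose of Repatha at any time during pregnancy or breastfeeding is classified as exposure". Sections 7.2 and 9.7.2.3.2 place women dosed during pregnancy and/or breast-feeding in the exposed group. Section 8.2 defines exposure for pregnancy outcomes more narrowly, as 15 weeks before or during pregnancy.

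Section 9.7.2.7 states: "Results from mothers are to be presented using the following columns". There are eight columns. Column (v) covers women treated at conception and in the first "trimester but stopped during 2 nd /3 rd trimesters". The next two are labelled "vi) 'exposed throughout pregnancy', (vii) 'exposure during breastfeeding only". The columns may overlap. No rule requires a dose to precede the outcome, and Sections 9.7.2.5 and 9.7.2.7.2 plan no sensitivity analysis.

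**The concern.** Both complications arise while the pregnancy continues, so dosing can change after the diagnosis. Columns (v), (vi) and (vii) can be assigned only once later dosing is known. That has three consequences for these outcomes:

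- A woman first dosed after her diagnosis is a case in the second/third-trimester column, although the event came before the exposure.
- A woman whose dosing ends at, or because of, the diagnosis cannot be in column (vi) and becomes a case in column (v). Her exposure up to the event may have matched that of a woman who stays in (vi).
- A woman first dosed while breast-feeding appears in an exposure-timing column, although any complication of that pregnancy preceded every dose.

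Percentages by exposure timing are what the study delivers on maternal complications. Nothing is tested or adjusted, so nothing later in the analysis would correct a column that depends partly on the outcome.

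**Working it through.** The plan states no complication rate, stopping rate or sample-size figure on which this point depends, so there is no figure of its own to reproduce. The check has three parts.

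**1. Breastfeeding-only women (no assumption needed).** Under Section 8.2 a woman with no dose in the 15 weeks before or during pregnancy is unexposed for pregnancy outcomes. Under Sections 7.2 and 9.7.2.3.2 the same woman is exposed if dosed while breast-feeding, and Section 9.7.2.7 gives her column (vii). The passages disagree about her.

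**2. Movement between (vi) and (v).** Columns may overlap, but stopping in the second or third trimester and being treated throughout exclude each other. Assume no drug effect and n women dosed at conception and in the first trimester. Let p be the complication risk, s0 the probability of stopping without the event, and s1 the probability with it. Then:

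- risk in (v) = p·s1 / [p·s1 + (1−p)·s0]
- risk in (vi) = p·(1−s1) / [p·(1−s1) + (1−p)·(1−s0)]

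The first exceeds the second exactly when s1 > s0, so the direction depends only on whether cases stop more often than non-cases. With n = 300 (the Section 9.5 target, used only for scale) and assumed rates:

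| p | s0 | s1 | (v) | (vi) | ratio |
|---|---|---|---|---|---|
| 5% | 50% | 50% | 7.5/150 = 5.0% | 7.5/150 = 5.0% | 1.00 |
| 10% | 70% | 80% | 24/213 = 11.3% | 6/87 = 6.9% | 1.63 |
| 5% | 50% | 80% | 12/154.5 = 7.8% | 3/145.5 = 2.1% | 3.77 |
| 5% | 30% | 80% | 12/97.5 = 12.3% | 3/202.5 = 1.5% | 8.31 |
| 3% | 30% | 95% | 8.55/95.85 = 8.9% | 0.45/204.15 = 0.2% | 40.5 |

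Over p of 3–10%, s0 of 30–70% and s1 of 80–95%, the ratio runs from 1.63 to 40.5, while the true ratio is 1.00.

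A second set-up takes 100 women and p = 5%. Some stop for unrelated reasons, and a share q of the remaining cases stops at diagnosis.

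- 10 unrelated stoppers, q = 25%: (v) = (0.5 + 1.125)/11.125 = 14.6%; (vi) = 3.375/88.875 = 3.8%; ratio 3.8.
- 10 unrelated stoppers, q = 75%: (v) = (0.5 + 3.375)/13.375 = 29.0%; (vi) = 1.125/86.625 = 1.3%; ratio 22.
- 50 unrelated stoppers, q = 25%: (v) = (2.5 + 0.625)/50.625 = 6.2%; (vi) = 1.875/49.375 = 3.8%; ratio 1.6.
- q = 0: ratio 1.0.

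**3. Which repair works.** Truncating dosing at diagnosis for cases only does not. Take 100 women, p = 5%, half stopping for unrelated reasons and, at the extreme, all of that after diagnosis. The 5 cases are frozen as treated throughout, while 47.5 of the 95 non-cases move to stopped. Column (vi) becomes 5/52.5 = 9.5% and column (v) 0/47.5 = 0%, again with no drug effect.

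Classifying everyone at one gestational time point avoids this. If E exposed and U unexposed women are event-free then and share a later risk r, the groups show rE/E = r and rU/U = r.

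**The case against.** The strongest reply is that dates may well exist. The eCRF is not shown, and Section 9.3 is a list of data items. Section 11.1.1 requires all adverse events in exposed women to be reported, Section 11.2 refers to an Event eCRF, and the sample form in Appendix C has a start date and a box for events before the first dose. This stands against the inference a reader might draw that no diagnosis date is recorded at all; the documents do not show that. It does not remove the point. Section 11 limits safety reporting to exposed women, Section 9.7.3 plans no other safety analysis, and nothing links these dates to the columns.

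A second reply is that derivation rules belong in an analysis plan, which is not shown. That would be a natural place for the rule. But Section 9.7.2.7 is not silent: it sets the columns, and applying them as written produces the problem.

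Third, the Appendix G template has no row for these complications, so their place in the columns rests on the general sentence about mothers. True, but that sentence covers them, and the template is only an example.

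Fourth, stopped and throughout are undefined. If a dose carries exposure for 15 weeks, as Section 9.3.1 suggests, a woman stopping at week 30 stays exposed to week 45, beyond term. On that reading the shift is confined to last doses more than 15 weeks before delivery. This narrows the effect, and it also shows that the columns need a definition.

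Fifth, the label of column (vii) itself signals that exposure came after pregnancy. This softens the risk of misreading but leaves the conflict with Section 8.2.

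**Conclusion.** The point holds as a fault in exposure classification for two secondary outcomes. The outcome sections specify no timing, and the columns depend on dosing that may follow the event. The column (vii) inconsistency rests on the text alone. The shift from (vi) to (v) needs one assumption, that cases stop more often than non-cases; its direction then follows.

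Its size is unknown. A reader might infer a 4- to 22-fold distortion from the illustration with 10 unrelated stoppers per 100, but the documents do not support that figure. They do not say that either complication prompts stopping. Because the quoted product information (Section 7.1) restricts use in pregnancy, frequent unrelated stopping is plausible, and at 50 per 100 the ratio falls to 1.6. That is the low end of the settings tried and not a floor: the ratio is 1.0 if the event never prompts stopping.

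Nor does the plan contain a biased test. The study is descriptive and plans no formal comparison. The harm is column percentages that can mislead, which is worth mending because the remedy is cheap.

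**What to change.** 1. In Sections 9.3 and 9.3.2, add the date or gestational week of first diagnosis of pre-eclampsia and of gestational diabetes, for all women, exposed or not.
2. In Section 9.7.2.7 or the analysis plan, state that for these outcomes cases and non-cases alike are classified by exposure up to a common gestational time point fixed in advance. Include women still pregnant and event-free at that point, and count only later events. Person-time by time-varying exposure is an alternative.
3. Do not report these outcomes by columns (v) and (vi). List events before the time point or before the first dose separately, and give undated events their own line.
4. For these outcomes, count women dosed only while breast-feeding as unexposed in pregnancy, in line with Section 8.2.

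The cost is one field per complication, drawn from maternity records that Section 9.4 already expects to be available, plus one extra derivation and a small undated category. Early events leave the main percentage and are seen only in the separate listing. The change does not deal with confounding between women who continue and women who stop. It alters neither treatment nor enrolment.
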